7.2.2 Safety and tolerability assessments

Safety will be monitored by the assessments described below as well as the collection of AEs at every visit. For details on AE collection and reporting, refer to [Section 8](#). Significant findings that were present prior to the signing of informed consent must be included in the relevant medical history/current medical conditions page on the patient's eCRF. Significant new findings that begin or worsen after informed consent must be recorded on the Adverse Event page of the patient's eCRF.

[figure not shown]
7.2.2.1 Physical examination

Physical examinations will include an examination of general appearance, skin, neck (including thyroid), eyes, ears, nose, throat, lungs, heart, abdomen, back, lymph nodes, extremities, and a basic nervous system evaluation. Information about the physical examination must be present in the source documentation at the study center. For the assessment schedule refer to [Table 7-1](#).

Significant findings that were present prior to the signing of informed consent must be included in the Medical History page on the patient's eCRF. Significant new findings that begin or worsen after informed consent must be recorded on the Adverse Event page of the patient's eCRF.

7.2.2.2 Vital signs

Vital signs include body temperature, blood pressure and pulse measurements. Blood pressure (systolic and diastolic) and pulse should be measured after the patient has been sitting for five minutes.

For the assessment schedule refer to [Table 7-1](#).

7.2.2.3 Height and weight

Height in centimeters (cm) and body weight (to the nearest 0.1 kilogram [kg] in indoor clothing, but without shoes) will be measured. Height will be measured at screening only. For the assessment schedule for weight refer to [Table 7-1](#).

7.2.2.4 Performance status

WHO performance status will be assessed as per the assessment schedule (refer to [Table 7-1](#)).

Assessment of WHO performance status ([Table 7-2](#)) will be performed within the time windows described above of the scheduled assessment, even if study medication is being held. More frequent examinations may be performed at the investigator's discretion, if medically indicated.

Table 7-2 WHO performance status scale

Score	Performance Status
0	Fully active, able to carry on all pre-disease performance without restriction
1	Restricted in physically strenuous activity but ambulatory and able to carry out work of a light or sedentary nature, e.g. light housework, office work
2	Ambulatory and capable of all self-care but unable to carry out any work activities. Up and about more than 50% of waking hours
3	Capable of only limited self-care, confined to bed or chair more than 50% of waking hours
4	Completely disabled. Cannot carry on any self-care. Totally confined to bed or chair
5	Dead

7.2.2.5 Laboratory evaluations

Central laboratories will be used for the analysis of scheduled hematology, biochemistry and other blood specimens collected as part as safety monitoring. All unscheduled blood testing will be performed locally. Dipstick urinalysis will be performed locally, except in the case of any out of range parameter on scheduled local urine analysis, when a urine sample will be sent to central laboratory for further analysis. Details on the collection, shipment of blood, urine and tumor samples and reporting of results by the central laboratory are provided to investigators in a separate [\[Laboratory Manual\]](#). The time windows granted for laboratory evaluations are identical to the corresponding visit time windows for each visit (refer to [Section 7.1](#)).

Laboratory values obtained at the screening visit will be used to assess eligibility to meet inclusion criteria 7. In addition, eligible patients must have baseline laboratory assessments performed on Cycle 1 Day 1 / Run-in Day 1 or within 24 hours prior to dosing. The results of centrally-analyzed laboratory assessments performed at Cycle 1 Day 1 do not need to be received by the site prior to initiation of dosing.

[figure not shown]

Table 7-3 Clinical laboratory parameters collection plan

Test Category	Test Name
Hematology	Hemoglobin, platelets, white blood cells (WBC), red blood cells (RBC), differential (basophils, eosinophils, lymphocytes, monocytes, neutrophils [% or absolute])
Blood Chemistry	Albumin, ALT, AST, calcium (at screening calcium corrected for albumin), creatinine, creatinine clearance, total bilirubin, direct bilirubin (only if total bilirubin is \geq grade 2), blood urea nitrogen (BUN) or urea, magnesium, potassium, sodium, fasting glucose, phosphate (inorganic phosphorus), alkaline phosphatase, amylase, GGT, lipase
Urinalysis	Macroscopic panel (dipstick) (bilirubin, blood, glucose, ketones, WBC, pH, protein, specific gravity) Microscopic panel (RBC, WBC, casts)
Hormones (males only)	Testosterone, LH, FSH, sex hormone binding globulin (SHBG)
Coagulation	INR and pro-thrombin time (PT) or Quick Test

Details on the collections, shipment of samples and reporting of results by the central laboratory are provided to investigators in the [Laboratory Manual].

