
Inclusion criteria
	
 • Histologically or cytologically confirmed diagnosis of stage IIIB or IV NSCLC that carries an ALK rearrangement, as per the FDA-approved Vysis ALK break-apart FISH assay (Abbott Molecular Inc.). • Age 18 years or older at the time of informed consent. • Patients must have stage IIIB or IV NSCLC. • Patients may have received up to 3 lines of cytotoxic chemotherapy to treat their stage IIIB or IV NSCLC • Patients who have been treated with chemotherapy must have progressed during or after the last chemotherapy regimen received prior to the first dose of LDK378 • Patients must have a tumor tissue sample available, preferably being a new biopsy but otherwise being an archival sample collected either at the time of diagnosis of NSCLC or any time since, for assessing ALK rearrangements using the FDA-approved Vysis ALK break-apart FISH assay. • Patients must have recovered from all toxicities related to prior anticancer therapies to grade ≤ 2, except for patients with grade 2 nausea/vomiting and/or grade 2 diarrhea despite optimal supportive therapy who will not be allowed to participate in the study.

Exclusion criteria
	
 • Prior treatment with crizotinib, or any other ALK inhibitor investigational agent, for NSCLC • Patients with known hypersensitivity to any of the excipients of LDK378. • Patients with symptomatic central nervous system (CNS) metastases who are neurologically unstable or have required increasing doses of steroids within the 2 weeks prior to study entry to manage CNS symptoms. • History of carcinomatous meningitis. • Presence or history of a malignant disease other than NSCLC that has been diagnosed and/or required therapy within the past 3 years. • Clinically significant, uncontrolled heart disease.

Investigational and reference therapy
	
LDK378

Efficacy assessments
	
Tumor assessment by RECIST 1.1 as evaluated by investigator and by a BIRC

Safety assessments
	
 • Hematology, biochemistry, urinalysis, coagulation, pregnancy test and hormones (males only) • ECG • Performance status • Vital signs • Adverse events

Other assessments
	
 • Trough and sparse PK

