7.1 Study flow and visit schedule

Table 7-1 lists all of the assessments and indicates with an “X” the visits when they are performed. Each treatment cycle is 28 days (the 28 days cycle length is fixed regardless of whether the dose of LDK378 is withheld). All visits are to be scheduled according to the appropriate number of calendar days from Cycle 1 Day 1 of study drug administration. A visit window of +/- 1 day in Cycle 1 and +/- 3 days in Cycle 2 onwards is allowed. Imaging evaluations may be performed +/-7 days of the due date of the assessment. **Note: If treatment with LDK378 is withheld at any time during the study, all study visits, safety and efficacy assessments should continue according to the appropriate number of calendar days from Cycle 1 Day 1 as per the schedule of assessments.**

All data obtained from these assessments must be supported in the patient’s source documentation. eCRF will not be used as a source document. The table indicates which assessments produce data to be entered into the database (D) or remain in the source documents only (S).

[figure not shown]
[figure not shown]
[figure not shown]

Table 7-1 Visit evaluation schedule

[figure not shown]
	Category	Protocol section	Screening Phase		Treatment Phase			Post treatment efficacy/ follow up phase		Survival follow-up phase	
					Cycle 1 (28 d)		Subsequent cycles (28 d)				End of study treatment (EOT)
Visit name			Molecular pre-screen	Screening Visit (Day -28 to Day -1)	Cycle 1 Day 1	Cycle 1 Day 15	Cycle 2 Day 1; Cycle 3 Day 1; etc.	End of treatment visit	Tumor follow-up	Study phase completion	Survival follow-up
Obtain pre-screening informed consent	D		X								
Obtain Main Informed Consent	D	11.3.		X							
Confirmation of ALK status by central laboratory	D	7.1.1.	New biopsy preferred and/or archival tissue & pathology report								
End of Phase Disposition Page	D	7.1.		X				X		X	
Patient history											
Demography	D	7.1.2.3.		X							
Inclusion/ exclusion criteria	D	5.2. 5.3.		X							
Eligibility check	S	7.1.2.1.		X							
Relevant medical history/ current medical conditions	D	7.1.2.3.		X							

[figure not shown]
Visit name	Category	Protocol section	Screening Phase		Treatment Phase				Post treatment efficacy/ follow up phase		Survival follow-up phase
					Cycle 1 (28 d)		Subsequent cycles (28 d)	End of study treatment (EOT)			

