7.2.2.5.4 Pregnancy and assessments of fertility

All women of childbearing potential must complete a serum pregnancy test at the screening visit, at Cycle 1 Day 1, at every cycle throughout the study and at End of Treatment. Central laboratories will be used for the analysis of serum pregnancy tests.

Women who are determined not to be of child bearing potential before the study will only be tested at screening. When non-child bearing potential status is determined during the study, further pregnancy testing will not be continued. Women are considered post-menopausal if they have had 12 months of natural (spontaneous) amenorrhea with an appropriate clinical profile (e.g. age appropriate, history of vasomotor symptoms), and otherwise not of child bearing potential if they have had surgical bilateral oophorectomy (with or without hysterectomy) or tubal ligation at least six weeks ago. In the case of bilateral oophorectomy alone, only when the reproductive status of the woman has been confirmed by follow up hormone level assessment is she considered not of child bearing potential (such testing is not covered as part of the study assessments).

The time windows granted for pregnancy testing are identical to the corresponding visit time windows for each visit. Refer to [Table 7-1](#).

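### Low priority: on the natural reading of Protocol 7.2.2.5 and 7.2.2.5.4, a woman of childbearing potential may take her first dose before the Cycle 1 Day 1 serum pregnancy result is known

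*Protocol*

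**What the plan says.** Protocol section 7.2.2.5 sets the general laboratory rules. "Central laboratories will be used for the analysis of scheduled hematology, biochemistry and other blood specimens collected as part as safety monitoring". Screening values decide eligibility under inclusion criterion 7. Eligible patients also need baseline laboratory assessments "performed on Cycle 1 Day 1 / Run-in Day 1 or within 24 hours prior to dosing". The section then says that the results of centrally analyzed "laboratory assessments performed at Cycle 1 Day 1 do not need to be received by the site prior to initiation of dosing".

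Section 7.2.2.5.4, which sits under 7.2.2.5, covers pregnancy. Its rule for those who could conceive is that they "must complete a serum pregnancy test at the screening visit, at Cycle 1 Day 1, at every cycle throughout the study"; a last test follows when treatment ends. On where the samples are read, it says: "Central laboratories will be used for the analysis of serum pregnancy tests". On timing, "The time windows granted for pregnancy testing are identical to the corresponding visit time windows for each visit"; section 7.1 gives "A visit window of +/- 1 day in Cycle 1".

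Other places bear on the point:
- Section 4.1 and Table 7-1 let screening start as early as 28 days before the first dose.
- Exclusion criterion 14 bars pregnant women and sets no limit on the age of the test.
- Exclusion criterion 15 requires highly effective contraception.
- Pregnancy is a mandatory reason to stop treatment (7.1.4.1) and leads to withdrawal (8.4).

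**The concern.** For hematology and chemistry the waiver is sensible. Eligibility on those values is settled at screening, and the Day 1 sample serves as a baseline. Pregnancy is different. It is an absolute exclusion and a reason to stop treatment at once, and the protocol is otherwise cautious about reproductive exposure. Scheduling a Day 1 pregnancy test and then allowing the first dose before it is read does not fit that caution.

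The woman at stake conceived after the screening sample, or was too early in pregnancy to be detected then. Section 1.1.3 notes that ALK-positive patients are often younger, so childbearing potential is a realistic consideration. The point concerns patient safety only and has no bearing on sample size, power or type I error.

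**Working it through.** **Step 1: does the waiver reach the pregnancy test?** The waiver has two conditions: central analysis, and performance at Cycle 1 Day 1. Section 7.2.2.5.4 meets both.

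- *For inclusion:* 7.2.2.5.4 is a subsection of 7.2.2.5, Table 7-1 puts the pregnancy test under laboratory assessments, and the Protocol summary lists it among the safety assessments next to hematology and biochemistry.
- *Against inclusion:* Table 7-3, the list of laboratory parameters, omits it.
- *Result:* the wording covers the test, but no sentence says so outright.

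**Step 2: does anything else require a newer result?**

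| Place | What it requires before the first dose |
|---|---|
| Exclusion 14 | not pregnant; no limit on age of test |
| 7.1.2.1 | eligibility check after screening procedures |
| 6.4.1 | IRT contact at Cycle 1 Day 1; no pregnancy result mentioned |
| 7.2.2.5.4 | Day 1 sample taken; nothing on receiving its result |

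No local or urine test before dosing is specified. The screening result is therefore the only one that has to be known, and that too is inferred, from exclusion 14 and the eligibility check.

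**Step 3: age of that result.** Screening runs from Day -28 to Day -1, so the result is between 1 and 28 days old at first dose.

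**Step 4: avoidable exposure if the Day 1 sample is positive.** The sample is drawn whether or not its result is awaited, so exposure runs from first dose to receipt of the central result:

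exposure ≈ T × 750 mg, where T is the number of days from first dose to result.

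The 750 mg daily dose is from section 6.1.1. T is not in the documents; 1 to 7 days is an assumption.

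| Assumed T (days) | Doses | Exposure (mg) |
|---|---|---|
| 1 | 1 | 1 × 750 = 750 |
| 3 | 3 | 3 × 750 = 2,250 |
| 7 | 7 | 7 × 750 = 5,250 |

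**Step 5: number of women affected.** This cannot be derived. The documents give neither the number of women of childbearing potential nor a conception rate.

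**The case against.** The strongest objection is that nobody in this trial can benefit. The Amendment 4 rationale says recruitment is complete with 124 patients treated, and SAP section 2.1 ties the final cut-off of 22-Jan-2018 to the last patient's last visit. This stands, and it is the main reason for the low priority.

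Second, the waiver may be narrower than it looks. Its paragraph opens with inclusion criterion 7, which concerns blood counts and chemistry, and Table 7-3 leaves pregnancy out. Section 7.2.2.5.4 also states its own rules on central analysis and windows. That reading is plausible. It shows that the text is unclear, but it supplies no requirement to wait for the Day 1 result.

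Third, other controls exist. Section 5.1 makes the investigator responsible for treating only patients who meet no exclusion criterion. Unscheduled blood tests are done locally, so a site in doubt can test at once. Exclusion 15 requires highly effective contraception, and pill users must have been stable for at least 3 months. These lower the risk, but none of them makes a result newer than screening a condition of dosing.

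Fourth, milligrams of drug do not measure fetal risk, and the toxicology text in section 1.2.1.1.4 is not readable in the public document. This stands too. The figures in the working describe exposure only.

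A reader might go further and infer that a pregnant woman could be exposed for 28 days before anyone knew. The documents do not support that: 28 days is the maximum age of the screening result, while the Day 1 sample is still drawn and read. Nor do they show that any woman was dosed without a Day 1 result. The Laboratory Manual and the IRT manual are not available here and may hold a safeguard.

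**Conclusion.** The point holds as a low-priority wording gap. Read naturally, the protocol allows a first dose before a scheduled test that bears on an absolute exclusion has been read, with reliance on a screening result up to 28 days old. The avoidable exposure is roughly the central turnaround time, or 750 to 5,250 mg if that is 1 to 7 days.

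This rests on three assumptions: that the waiver covers the pregnancy test, which is inferred; that turnaround lies in the assumed range; and that no unseen manual adds a check. The claim is about the protocol text, not about what sites did.

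**What to change.** Keep the draw on Cycle 1 Day 1, or within 24 hours before dosing, mandatory. After the waiver sentence in 7.2.2.5, add:

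*This waiver does not apply to the pregnancy test: for women of childbearing potential, a negative result from the Cycle 1 Day 1 sample (or one taken within 24 hours before dosing) must be available before the first dose. This sample may be analyzed locally.*

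Repeat the rule in 7.2.2.5.4, where it is needed as an exception to central analysis, and as a footnote to the pregnancy row of Table 7-1. The 24-hour limit and the Cycle 1 visit window need no relaxation, because the required sample lies inside both.

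A look-back window, such as accepting any negative result from the previous 7 days, is a tempting alternative but should be avoided. If the earlier sample replaced the Day 1 draw, a pregnancy first detectable in between would not be tested for again until Cycle 2 Day 1. That is about 28 doses, or 28 × 750 = 21,000 mg, which is worse than the present text.

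The cost is one addition to 7.2.2.5, its repetition in 7.2.2.5.4 and one footnote. For women of childbearing potential it means local analysis of a sample already scheduled, or a short delay of the first dose. A very early pregnancy can still be missed. With recruitment complete, the change corrects the text and any later protocol that reuses it.

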7.2.2.5.1 Hematology

Hematology assessments of the parameters listed in Table 7-3 will be tested as per the schedule of assessments (Table 7-1).

7.2.2.5.2 Blood chemistry

Blood chemistry assessments of the parameters listed in Table 7-3 will be tested as per the schedule of assessments (Table 7-1).

7.2.2.5.3 Urinalysis

Dipstick measurements will be performed as per Table 7-3 and according to the schedule of assessments. Any significant findings on dipstick will be followed up with microscopic evaluation as per Table 7-3.

7.2.2.5.4 Pregnancy and assessments of fertility

All women of childbearing potential must complete a serum pregnancy test at the screening visit, at Cycle 1 Day 1, at every cycle throughout the study and at End of Treatment. Central laboratories will be used for the analysis of serum pregnancy tests.

Women who are determined not to be of child bearing potential before the study will only be tested at screening. When non-child bearing potential status is determined during the study, further pregnancy testing will not be continued. Women are considered post-menopausal if they have had 12 months of natural (spontaneous) amenorrhea with an appropriate clinical profile (e.g. age appropriate, history of vasomotor symptoms), and otherwise not of child bearing potential if they have had surgical bilateral oophorectomy (with or without hysterectomy) or tubal ligation at least six weeks ago. In the case of bilateral oophorectomy alone, only when the reproductive status of the woman has been confirmed by follow up hormone level assessment is she considered not of child bearing potential (such testing is not covered as part of the study assessments).

The time windows granted for pregnancy testing are identical to the corresponding visit time windows for each visit. Refer to [Table 7-1](#).

7.2.2.5.5 Hormones

Testosterone, LH, FSH and sex hormone binding globulin (SHBG) will be tested in male patients only and as per the schedule of assessments ([Table 7-1](#)).

7.2.2.5.6 Coagulation

INR and pro-thrombin time (PT) or Quick Test will be measured at screening only.

7.2.2.6 Cardiac assessments

[figure not shown]
7.2.2.6.1 Electrocardiogram (ECG)

[figure not shown]
[figure not shown]
A standard 12 lead ECG will be performed

[figure not shown]
[figure not shown]
- At the screening visit, in triplicate.
- At Cycle 1 Day 1, in triplicate, pre-dose, and in triplicate 6 hours (+/- 30 minutes) after dosing.
- At Cycle 1 Day 15 and at Cycle 2 Day 1 in triplicate, pre-dose.
- [REDACTED]
- At other defined timepoints (Day 1 of subsequent cycles) (see [Table 7-1](#)) as single ECGs, pre-dose.

[figure not shown]
[figure not shown]
ECGs will be performed in supine position. All ECGs recorded for each time point will be transmitted electronically to a central laboratory and will be centrally reviewed by an independent reviewer. Any original ECG not transmitted electronically to the central laboratory should be forwarded for central review.

[figure not shown]
Interpretation of the tracing must be made by a qualified physician. Each ECG tracing should be labeled with the study number, patient initials (where regulations permit), patient number, date, and kept in the source documents at the study site. Clinically significant abnormalities present when the patient signed informed consent should be reported on the Medical History eCRF page. Clinically significant findings must be discussed with Novartis prior to enrolling the patient in the study. New or worsened clinically significant findings occurring after informed consent must be recorded on the Adverse Events eCRF page. When triplicate ECGs are taken, for the purposes of inclusion criteria and dose level management, mean parameter values should be used.

[figure not shown]
[figure not shown]

7.2.5 Resource utilization

Not applicable.

8 Safety monitoring and reporting

8.1 Adverse events (AEs)

8.1.1 Definitions and reporting

An AE is defined as the appearance of (or worsening of any pre-existing) undesirable sign(s), symptom(s), or medical condition(s) that occur after patient's signed informed consent has been obtained.

Abnormal laboratory values or test results occurring after informed consent constitute AEs only if they induce clinical signs or symptoms, are considered clinically significant, require therapy (e.g., hematologic abnormality that requires transfusion or hematological stem cell support), or require changes in study medication(s).

AEs that begin or worsen after informed consent has been obtained should be recorded in the Adverse Events eCRF. Conditions that were already present at the time of informed consent should be recorded in the Medical History page of the patient's eCRF. AE monitoring should be continued for at least 30 days following the last dose of study treatment. AEs (including lab abnormalities that constitute AEs) should be described using a diagnosis whenever possible, rather than individual underlying signs and symptoms. When a clear diagnosis cannot be identified, each sign or symptom should be reported as a separate AE.

AEs will be assessed according to the Common Terminology Criteria for Adverse Events (CTCAE) version 4.03 (dated 14 June 2010). If CTCAE grading does not exist for an AE, the severity of mild, moderate, severe, and life-threatening, corresponding to Grades 1 - 4, will be used. CTCAE Grade 5 (death) will not be used in this study; rather, information about deaths will be collected through a Death eCRF. The occurrence of AEs should be sought by non-directive questioning of the patient during the screening process after signing informed consent and at each visit during the study. AEs also may be detected when they are volunteered by the patient during the screening process or between visits, or through physical examination, laboratory test, or other assessments. As far as possible, each AE should be evaluated to determine:

1. The severity grade (CTCAE Grade 1-4)
2. Its duration (Start and end dates)

3. Its relationship to the study treatment (Reasonable possibility that AE is related: No, Yes)
4. Action taken with respect to study or investigational treatment (none, dose adjusted, temporarily interrupted, permanently discontinued, unknown, not applicable)
5. Whether medication or therapy was given (no concomitant medication/non-drug therapy, concomitant medication/non-drug therapy)
6. Outcome (not recovered/not resolved, recovered/resolved, recovering/resolving, recovered/resolved with sequelae, fatal, unknown)
7. Whether it is serious, where a serious AE (SAE) is defined as in [Section 8.2.1](#).

All AEs should be treated appropriately. If a concomitant medication or non-drug therapy is given, this action should be recorded on the Adverse Event eCRF.

Once an AE is detected, it should be followed until its resolution or until it is judged to be permanent, and assessment should be made at each visit (or more frequently, if necessary) of any changes in severity, the suspected relationship to the study treatment, the interventions required to treat it, and the outcome.

Progression of malignancy (including fatal outcomes), if documented by use of appropriate method (for example, as per RECIST criteria for solid tumors), should not be reported as a SAE.

AEs separate from the progression of malignancy (example, deep vein thrombosis at the time of progression or hemoptysis concurrent with finding of disease progression) will be reported as per usual guidelines used for such events with proper attribution regarding relatedness to the drug.

